5.3 Masking

This trial will be single masked, with most members of the study team including the lead biostatistician masked to the comparator group (treatment condition) randomly assigned to each participant. Due to the nature of the intervention, masking providers or study participants to the comparator received is not feasible. The PI and research coordination team will conduct study enrollment and fidelity monitoring activities that may reveal the treatment assignment of individual participants.

6. Study Population

The primary study population for this research is adult and adolescent patients in Emergency Departments and primary care settings in the St. Luke's Health System who are identified as being at risk for suicide and have a completed Safety Plan or Connection & Support Plan.¹

This study will recruit 1,382 participants (790 adults and 592 adolescents) from 32 clinical sites:

9 EDs and 23 primary care clinics.

The secondary study population for this research consists of providers and clinical staff at study sites. This population will be recruited to participate through email invitation. Employee email addresses will be obtained, for example, through the use of site champions/liaisons or Digital and Analytics analysts. Although there is no estimated sample size for this population, sufficient participation is anticipated to complete Aim 2 of this protocol.

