6.4 Populations for Analyses

Analyses will be completed using the following populations:

1. **Intention to Treat (ITT) Analytic Population:** Data for all participants that complete study enrollment will be included in this dataset.
2. **Safety Analysis Population:** The dataset shared with the Data & Safety Monitoring Board for safety analysis will include data for all participants who completed study enrollment (e.g., the ITT Analytic Population Dataset).
3. **Per-Protocol Analysis Population:** Data for a subset of participants who were retained for the duration of the study and completed the minimum assigned intervention (e.g. received at least one phone call (SPI+), or were sent at least 4 caring contacts (SP+CC)).
4. **Additional Populations:** Additional datasets may be developed to complete sensitivity analyses, for example, where missing data have been imputed using different techniques.

7. Study Procedures

Pre-Consent – All participants (All activities are standard of care)

- C-SSRS screening for suicide risk at clinic or ED visit
- Development of safety plan or a connection and support plan

Baseline / Enrollment Visit – All participants (During/following clinic or ED visit)

- Study enrollment and informed consent
- Baseline Survey
 - Baseline survey includes questions related to demographics, socioeconomic status, gender identity, sexuality, religion, drug and alcohol use, quality of life, loneliness, self-harm and suicidal behavior.

Follow-Up Intervention – SPI+ participants

- Follow-up phone calls from the Hotline
 - 1 call within 72 hours of study enrollment to connect with the participant.
 - Series of 1-6 phone calls, based on participant's preference.
 - See *Description of Interventions*.

Follow-Up Intervention – SP+CC participants

- Follow-up phone call and caring text or email messages from the Hotline
 - 1 call within 72 hours of study enrollment to connect with the participant.
 - 25 personalized caring text or email messages sent according to a standardized schedule over a 12-month period.
 - See *Description of Interventions*.

2-Week Patient Satisfaction Survey – All participants (REDCap survey link sent via text or email)

- Patient satisfaction survey related to intervention received

6 Month Outcome Assessment – All participants (+ 4 weeks variance window) (REDCap survey link sent via email or text, or phone call)

- 6-Month Outcomes Survey

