The C-SSRS is available in a full-length version comprised of 11 yes/no questions plus 7 multiple choice questions and space to collect and record brief narrative explanations. An abbreviated screener version of the C-SSRS consists of 5 yes/no questions related to suicidal ideation and one two-part yes/no question related to suicidal behavior. Both the full-length and screener versions of the C-SSRS are available in a 'lifetime-recent' version (to establish a baseline) and a 'since last contact' version to be administered at follow-up visits. Two versions of the C-SSRS will be used for this study: C-SSRS Lifetime-Recent Screener (given at baseline, in accordance with standard of care at SLHS), and C-SSRS Since Last Contact Screener (given at 6 and 12 months). In addition to using the C-SSRS Screeners at baseline and follow-up, the study will incorporate three items from the full-version of the C-SSRS that are not included in the screener version to measure: (1) Aborted or self-interrupted suicide attempts; (2) interrupted suicide attempts; and (3) actual suicide attempts at baseline, 6, and 12 months. Non-lethal self-harm, lethal means used for attempts or completions, and death by suicide will also be collected. Vital records will be used to measure suicide completion.

In EDs, C-SSRS screening is routinely administered by nurses during triage as standard of care, while in primary care clinics the C-SSRS screener will be self-administered by patients. The C-SSRS delivered as standard of care in either setting will be used as the basis for determining eligibility for completing a safety plan and eligibility for study enrollment. However, in ED settings, the C-SSRS will be re-

administered in a self-complete format for study participants as part of their baseline surveys, from which change in severity of suicidality will be measured when they self-complete the C-SSRS as part of 6 and 12-month outcome surveys.

The two C-SSRS scores collected during the baseline visit in EDs (nurse-administered vs. self-administered) will be compared as a sub-analysis to assess for any systematic differences in score. The results of this sub-analysis may inform future clinical practice as it relates to C-SSRS administration in SLHS EDs and other settings.

Table 3: C-SSRS Screening Tools by Timepoint, SPARC Trial

Timepoint	C-SSRS Assessment Used
Baseline Survey	Lifetime-Recent C-SSRS Screener (6 questions)

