11.3 Lost to Follow-Up

A study participant will be considered lost to follow-up if s/he fails to complete both study follow-up assessments and study staff are unable to contact the participant after at least 3 attempts. The following actions must be taken before a participant will be declared lost to follow-up.

- Study staff will attempt to contact the participant, re-send the REDCap survey or reschedule the missed phone-based assessment, and ascertain whether the participant wishes to and/or should continue in the study
- The study staff will make every effort to regain contact with the participant (using text, email, phone call, and/or alternative means of contact).
- Should the participant continue to be unreachable, s/he will be considered lost to follow-up and will be withdrawn from the study.

12. Data & Safety Monitoring

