13.1 Data Collection

Baseline data are either already collected and recorded in EPIC as standard of care for all patients (demographic data, C-SSRS) or will be completed by the participant via REDCap survey immediately following enrollment and informed consent (Baseline Survey). Outcome data will be collected via REDCap survey or over the phone at 6 months and 12 months. *Table 4* includes a list of all study variables for the primary analysis, the tool to be used for data collection or source of the data, the frequency/timing with which they will be collected, whether they are routinely collected or will be collected specifically for the SPARC Trial, and which entity will collect them. Patient and provider satisfaction surveys will collect additional quantitative and qualitative data and will be collected via REDCap survey.

Table 4: SPARC Trial Variables of Interest and Other Data Elements

Variable	Tool/Source	Routinely collected as standard of care	Mode of contact	Who will collect
Outcomes (6 months)				
Suicidal ideation & behavior	C-SSRS	No	REDCap survey (text, email, or phone)	SLHS
Recent suicide attempts, suicide completion, & self-harm; lethal means	6- and 12-Months Suicide Attempts Survey, Vital Records, EPIC	No	REDCap survey (text, email, or phone)	SLHS
Loneliness	NIH Toolkit Loneliness Scale	No	REDCap survey (text, email, or phone)	SLHS
Uptake of outpatient mental health treatment	Self-report, EPIC, Claims data	Yes	REDCap survey (text, email, or phone)	SLHS

Return to ED for suicidality	Self-report, EPIC, EDIE, Claims data	Yes	REDCap survey (text, email, or phone)	SLHS
Outcomes (12 Months)				
Suicidal ideation & behavior	C-SSRS	No	REDCap survey (text, email, or phone)	SLHS
Recent suicide attempts, completion, & self-harm; lethal means	6- and 12-Months Suicide Attempts Survey; Vital Records, EPIC	No	REDCap survey (text, email, or phone)	SLHS
Loneliness	NIH Toolkit Loneliness Scale	No	REDCap survey (text, email, or phone)	SLHS
Uptake of outpatient mental health treatment	Self-report, EPIC, Claims data	Yes	REDCap survey (text, email, or phone)	SLHS
Return to ED for suicidality	Self-report, EPIC, Claims data, EDIE	Yes	REDCap survey (text, email, or phone)	SLHS

Exposures (Baseline)				
Age in years, age category (adult/peds)	EPIC	Yes	n/a	SLHS
Sex	EPIC	Yes	n/a	SLHS
Race and ethnicity	EPIC	Yes	n/a	SLHS
Address including Zip code of residence (urban/rural)	EPIC	Yes	n/a	SLHS
County of residence (urban/rural)	EPIC	Yes	n/a	SLHS

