16.1 Potential Risks

There are several potential risks to participation in this study. Loss of confidentiality due to the unintended release of sensitive information is one risk. This risk will be mitigated by storing all electronic data on password protected computers. Data will be shared among research partners through REDCap, Mosio, and other secure HIPAA-compliant means (such as secure email). REDCap is a secure, HIPAA-

compliant web-based research data management application, used for building and managing online surveys, and providing a secure electronic database. REDCap will be used as a central location for online study data storage and participant management.

Other potential risks include psychological distress from completing study questionnaires. The contact in the follow-up intervention may also cause emotional distress. Research participants will be reminded at enrollment that they may leave the study at any point with no consequences to the care they receive at SLHS and will be reminded of resources (such as the Hotline) that they can access as needed in the event of psychological distress.

Study staff (including anyone involved in enrollment and informed consent or delivery of the follow-up intervention or outcome measurements, and/or having access to patient-level data) will be trained on the protection of human subjects and HIPAA, with a focus on topics relevant to confidentiality. SLHS staff will assist participants in completing informed consent and baseline surveys, and survey links will be sent out via text or email, or study staff will assist participants in completing surveys over the phone. Study staff at SLHS, University of Washington and the Hotline will have access to protected health information (PHI).

The study is designed to be low burden in terms of participants' time. Patient participants will be compensated for their time. Providers who complete the Provider Satisfaction Survey will not be compensated for their time.

Patients will not be enrolled in the study if a provider or study staff determines that they are unable to consent to participate.

Participants will be under no duress or pressure to participate in or complete this study. Participating in this study will not impact the care they receive, and this will be clearly communicated to participants as part of the informed consent process.

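### The follow-up C-SSRS is described as self-completed, but the protocol also allows it by phone with study staff, some of whom may know the arm, so the primary outcome can be collected unmasked and in mixed modes

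*Protocol*

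**What the plan says.** On mode, Section 9.2 has the ED C-SSRS repeated at baseline, "administered in a self-complete format for study participants as part of their baseline surveys", and goes on: "from which change in severity of suicidality will be measured when they self-complete the C-SSRS as part of 6 and 12-month outcome surveys". The nurse-administered and self-administered ED scores "will be compared as a sub-analysis to assess for any systematic differences in score".

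Other sections describe the same follow-up surveys differently. Section 7 gives the route at both 6 and 12 months as "REDCap survey link sent via email or text, or phone call". Section 13.1 says "Outcome data will be collected via REDCap survey or over the phone at 6 months and 12 months". Section 11.3 tells staff to re-send the survey or "reschedule the missed phone-based assessment". Section 16.1 says survey links will be sent, or "study staff will assist participants in completing surveys over the phone". For baseline, Table 4 labels the repeated ED C-SSRS as self-report but lists in-person, phone and video contact as its routes.

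On masking, Section 5.3 masks most of the study team, including the lead biostatistician, does not mask participants or providers, and adds: "The PI and research coordination team will conduct study enrollment and fidelity monitoring activities that may reveal the treatment assignment of individual participants".

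**The concern.** Section 9.2 treats the way the C-SSRS is administered as something that may move the score. It repeats the ED measurement in the format intended for follow-up and plans a comparison of the two ED scores. A follow-up C-SSRS taken in conversation with staff is not obviously the same measurement as one answered privately through a link, because disclosure of suicidal thoughts may differ between the two.

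Two routes to bias in the arm comparison follow. First, a caller who knows the allocation can influence answers through tone, prompting or the recording of ambiguous replies. Second, if phone completion is more common in one arm, or affects answers differently by arm, a mode effect appears as a treatment difference. Both would act on the primary outcome of a trial whose stated hypothesis favours SP+CC.

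**Working it through.** The protocol gives no figure on this point to reproduce, so the main check sets its statements side by side.

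1. **Follow-up mode.** Section 9.2 describes self-completion. Sections 7, 11.3, 13.1 and 16.1 each provide for the phone. No section says which governs, calls phone a fallback, or says how phone and self-completed scores enter one change score.
2. **Baseline mode.** Primary care C-SSRS screening is self-administered. The repeated ED C-SSRS is called self-complete in Section 9.2, but Table 4 permits live contact for it. Mode is therefore not fixed at baseline either.
3. **Recording of mode.** Table 4 lists permitted routes for each variable but no data element for the route actually used for a given C-SSRS.
4. **Who may know the arm.** Section 5.3 names the PI and the research coordination team. Section 10.6 has study staff review SPI+ call templates, listen to calls and read SP+CC text exchanges, all of which identify the arm.
5. **Who takes the outcome.** Section 16.1 says study staff, and Table 4 says SLHS. Section 12.5 gives research coordinators as an example of personnel who may learn of urgent needs at enrolment or at an outcome assessment, which implies that they can be present at the latter. No statement separates callers from enrolment or fidelity staff.
6. **Unmasking within the call.** Sections 5.1.2 and 7 place satisfaction with the calls or messages received in the 12-month outcomes survey. The answers can reveal the arm even to a caller who began masked. Item order is not stated.

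For scale only, let f be the share of follow-ups by phone and b the net between-arm shift that callers cause, averaged over all phone follow-ups. Let d be the between-arm difference in phone share and m the shift of phone relative to self-completion. Then:

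- observer bias = f × b
- mode bias = d × m, if m is the same in both arms
- SE = SD × √(2/n)
- false-positive rate = 1 − Φ(1.96 − bias/SE) + Φ(−1.96 − bias/SE)

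From Section 14.2, SD = 2 and dropout is 30%. SD = 2 is taken as the SD of the analysed outcome, and clustering is ignored.

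- Adults: n = 790 × 0.7 / 2 = 276.5 per arm, SE = 2 × √(2/276.5) = 0.170.
- Adolescents: n = 592 × 0.7 / 2 = 207.2 per arm, SE = 2 × √(2/207.2) = 0.196.

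The values of f, b, d and m below are assumptions.

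| Assumed inputs | Bias (units) | False-positive rate, adults | False-positive rate, adolescents |
|---|---|---|---|
| f = 0.10, b = 0.25 | 0.025 | 5.2% | 5.2% |
| f = 0.30, b = 0.5 | 0.15 | 14.3% | 11.9% |
| f = 0.50, b = 0.5 | 0.25 | 31.2% | 24.6% |
| d = 0, m = 0.5 or 1 | 0 | 5.0% | 5.0% |
| d = 0.10, m = 0.5 | 0.05 | 6.0% | 5.7% |
| d = 0.10, m = 1 | 0.10 | 9.0% | 8.0% |
| d = 0.20, m = 1 | 0.20 | 21.7% | 17.5% |

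A mode effect alone leaves the arm contrast unbiased when phone use and its effect are equal across arms. The low end of the observer-bias range is negligible and the high end is not. Nothing in the protocol says where the trial would fall.

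**The case against.** The case on the other side has real force. A reader might draw four stronger conclusions, and the protocol supports none of them.

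- **That outcome masking is weaker than claimed.** Section 5.3 never claims masked outcome assessors. It openly discloses that the PI and coordinators may learn the arm, so there is no stronger promise to fall short of.
- **That phone completion does add observer bias.** The disclosure in Section 5.3 concerns enrolment and fidelity work. No section names who makes outcome calls, and operating procedures may settle it. Unmasked calling is permitted, not prescribed.
- **That phone follow-up restores the nurse-versus-self difference in the ED.** Section 9.2 contrasts self-completion with administration by triage nurses. Section 16.1 speaks of assisting participants, which is not clinician rating, and Table 4 already applies its self-report label to a survey taken with live contact. That the ED measurement is repeated in order to avoid a mode difference is also an inference, since the protocol gives no reason.
- **That a particular bias can be quoted.** A 0.15-unit bias is 15% of the 1-unit target in Section 14.2, but its inputs are assumed. A net shift of 0.5 units over all phone follow-ups would in effect require most callers to know the arm. That SP+CC participants answer links more readily is speculation: the caring messages come from the Hotline, while SLHS collects the surveys.

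The follow-up screener is also six fixed questions scored by the highest yes, which limits rater judgement. Participants know their arm, so reporting bias exists in every mode. A sensitivity analysis by mode could properly sit in an SAP that is not shown here.

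The inconsistent description of how the primary outcome is taken still stands, as does the absence of any rule separating callers from staff who may know the arm. Both are matters of trial conduct, which the protocol itself describes.

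**Conclusion.** The point holds as a conditional risk. Following the protocol as written allows the primary outcome to be taken by staff who may know the arm, in a mixture of modes that is not recorded for each assessment. Bias in the arm contrast follows only if callers know the arm and influence answers, or if phone use or its effect differs by arm. Otherwise, mixing modes shifts or adds noise to change scores in both arms.

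The size cannot be derived from the documents. The assumed ranges give 0.025 to 0.25 units for caller influence and 0.05 to 0.20 units for a mode effect with phone shares 10 to 20 points apart, and these illustrate scale only. The point does not show that the trial is biased. It supports an inexpensive improvement that keeps phone contact for retention.

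**What to change.** - Reconcile Section 9.2 with Sections 7, 11.3, 13.1, 16.1 and Table 4: self-completion by link as the default, phone as the fallback, with the same definition applied to the ED self-report baseline.
- Record the mode of every baseline and follow-up C-SSRS.
- Within the existing team and where feasible, assign outcome calls to staff who neither enrolled that participant nor reviewed their fidelity records. Hide allocation from the caller and have items read verbatim.
- At 12 months, ask the C-SSRS before the satisfaction items, since hiding allocation does not help once those answers reveal the arm.
- Examine the primary result by mode as a sensitivity analysis, in the protocol or the SAP.

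The cost is one data field, a call-assignment rule, a fixed item order and one additional analysis. The downside is slightly less flexible call scheduling. Team size is not given, so full separation of callers may not always be possible. None of this removes reporting bias from participants who know their arm.

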6.1 Inclusion & Exclusion Criteria

6.1.1 Selection of Study Sites

All SLHS EDs (n=9) and primary care clinics (n=53) were initially considered for inclusion as study sites. Sites located outside of Idaho (n=1) were excluded. Sites with enough patients screening positive for suicide annually (based on data from 2018) to enroll approximately 40 adults and/or 25 adolescents within approximately 12 months were considered eligible for inclusion.

6.1.1.1 Sites Selected for Inclusion in the Study

The 32 study sites were selected with an effort to identify sites representing a diversity of primary care practices (pediatrics, internal medicine, and family medicine), geographic locations, and populations. All EDs were included as study sites. Selected study sites were approved by Primary Care, Children's, and Acute Care Service Line Leaders and site-level leaders.

6.1.2 Study Participant Inclusion & Exclusion Criteria

Inclusion criteria are intentionally broad, to facilitate recruitment of a study sample that is maximally representative of the population of patients that SLHS serves.

Inclusion Criteria

- Patient at SLHS ED or primary care study site
- ≥ 12 years of age (adult ≥18 years of age or adolescent 12-17 years of age)
- Positive screen for suicidal ideation or behavior using C-SSRS (any C-SSRS score >0), or current /most recent visit is related to suicide attempt
- Completed safety plan or connection & support plan as part of current/most recent visit
- Access to a phone (cellular or landline) for the duration of the study with the ability to receive calls
- The ability to send and receive email messages (required) and text messages (optional)
- English or Spanish speaking and reading

Exclusion Criteria

- Patients who are unable or unwilling to provide informed consent to participate will be excluded

from the study.

- Examples may include but are not limited to patients who present with acute or chronic cognitive impairment that would preclude their ability to consent (i.e. acute psychosis, intoxication, or intellectual disability).
- Patients who are inappropriate for study participation based on provider clinical judgement.

6.1.3 Inclusion and Exclusion Criteria for Provider Satisfaction Survey

Inclusion Criteria

- Provider or clinical staff (such as physician, advanced practice provider, nurse, medical assistant, or social worker) at SLHS SPARC Trial Study Site
- Read and write in English

Exclusion Criteria

- Providers or staff who work at multiple study sites may only complete one survey, and it should be linked with the site at which they spend most time

